Successful completion of study enrollment includes consent process, baseline data collection, and issuance of group assignment and study cell phone,

Study team will create a ResearchMatch profile. ResearchMatch.org is a free, publically available, and secure online tool created which allows individuals to find research studies for which they may be eligible. All interested individuals indicating interest will be screened by study staff per current protocol.

Digital advertising (FB & Instagram ads) will be utilized to reach target population and will be targeted to 16-25 year olds within the Houston area. Individuals who respond to the ads via social media, phone, or email will be screened for eligibility by study staff and if eligible, will be invited to participate per current protocol.

If risk level for coronavirus according to Harris County is 2 or 3, study staff will set up tables outside of shelters or drop-in centers to engage potentially eligible youth, with permission from the agencies. Youth will be screened for eligibility on-site and if eligible, will be invited to participate per current protocol.

Study Procedures

Protection of Human Subjects from Research Risks

This Human Subjects research meets the definition of a clinical trial.

Human Subjects Involvement, Characteristics, and Design. This proposed randomized controlled trial will test the efficacy of a nurse case management (NCM) HIV prevention intervention compared to usual care among homeless young adults aged 16-25 years old. We will follow participants for 9 months after the intervention for a total study period of 12 months. The intervention incorporates motivational interviewing strategies combined with nurse case management and a smartphone based daily diary to develop participant driven HIV prevention behavioral goals. Given the inclusion criteria and volume of youth served at the recruitment sites, we expect to recruit 50 youth in YR-1, 200 youth in YR-2, 150 in YR-3 and 50 in YR-4 for a total sample size of 450. Youth will be recruited in partnership with the Salvation Army that runs a Young Adults Resource Drop-in Center and street outreach (see LOS), the Covenant House Texas (CHT) youth shelter and their street outreach program (see LOS), and the 13 free-standing and shelter-based Healthcare for the Homeless Program clinics ([name] is Medical Director and Co-I). As well, we will recruit from the 10 Legacy Federally Qualified Healthcare Center Clinics.

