Sources of Materials.

Baseline and Follow-up Survey Data. 5 Surveys will be collected at baseline, immediate, 3-, 6-, and 9-months post intervention using REDCap online surveys delivered on iPads or accessed remotely by participant smartphone or computer. Surveys will be provided in a quiet, private room at the drop-in center and shelter, and take about 30 minutes each to complete. In cases when a participant prefers to complete their survey at another location, the research assistant will find an agreed upon location to meet up with the youth to complete the survey such as a near-by library or coffee shop. For youth who leave the area during the data collection period, we will create an individualized survey link generated from REDCap. This web-based

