For HIV testing, we will use the INSTI HIV-1/HIV-2 Rapid Antibody Test (99.9% sensitivity, 100% specificity.) For Chlamydia and Gonorrhea, urine specimens will be collected in a sterile cup, refrigerated between 2°C to 8°C, and transported on the same day to Thomas Street Clinic, a Harris Health entity. Nurses will notify physician and Co-PI [name], who will order chlamydia and gonorrhea tests via the Harris Health lab. Results will be obtained by RNs credentialed by Harris Health via the electronic system, EPIC, and be shared with participants via phone call or in person. If collected at UTHealth, Chlamydia and Gonorrhea specimens will be processed via UTHealth clinic lab (LapCorp). For Syphilis testing, we will use the Syphilis Health Check, Syphilis Antibody Rapid Immunochromatographic Test. The assays will be run within 2 business days using the current laboratory procedures at Harris Health Systems (see Resources section). Specimens will be discarded based on the regulator laboratory procedures. Youth who test positive for an STI will be contacted to schedule a follow-up appointment to receive treatment as indicated. Reportable positive tests will be reported to the local health department to initiate partner notification procedures. Tests will be conducted in a private location in the drop-in center and shelter clinic area or private office space.

Preferred method for HIV & STI testing is conducted by study staff at recruitment site for convenience of participant. However, due to COVID-19 pandemic, study team will offer additional methods to conduct HIV & STI depending on current COVID-19 risk level, availability of PPE, health of study staff, health of participant, and location of participant:

- 1) With study staff at Cizik School of Nursing ([name] or [name])
- 2) Covenant House clinic
- 3) Harris Health clinic
- 4) At-home test to take under supervision of a study staff via video call.

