This intervention has 2 components: **(1) 6 Face-to-Face NCM Sessions** delivered by a nurse who will assist a participant to generate HIV prevention goal using Motivational Interviewing strategies and conduct an HIV risk profile and eligibility PrEP assessment. The nurse will meet the participant in a non-stigmatizing, trauma-informed way that respects where they are at in their current situation and evokes personal motivation for health promoting behaviors. Sessions are designed to meet the complex, multi-level health and social needs of homeless youth to align with the extant literature demonstrating the strong connection between HIV risk behaviors and mental health, substance use, and housing.¹ Therefore, at each session, the nurse will assess mental health, substance use, and housing needs to establish a plan of care with the participant. The nurse will coordinate health and social service navigation with the social workers at the agencies as needed with permission of the participant. The nurse will review HIV acquisition and transmission risk factors with the participant at each session and inquire about engagement in sexual risk behaviors since the last NCM session. During each NCM session and as needed, youth will complete an HIV risk profile used in the clinic setting to assess for PrEP eligibility based on the extent of behavioral risk. A screening tool developed from the Centers for Disease Control and Prevention 2014 Clinical Practice Guidelines for PrEP use will be used to assess PrEP eligibility based on HIV risk behaviors at the beginning of each NCM session to determine whether recent behaviors warrant PrEP as a possible intervention for HIV prevention. This includes having a HIV-positive sexual partner, recent bacterial STI, a high number of sex partners, a history of inconsistent or no condom use, or commercial sex work, and IV drug use. Houston, TX is considered a high HIV prevalence area and homeless youth are considered a high prevalence network. The nurse will use MI strategies to evoke participant generated HIV prevention goals and strategies. In the event that a participant is unable to attend a session in person, they will be offered the option of attending the session via video chat or phone, or meeting at a public location that is convenient for them such as a neighborhood library. Due to COVID-19, nurse may elect to deliver the intervention via video call depending on current COVID-19 risk level, availability of PPE, health of study staff, health of participant, and location of participant. **(2) Behavioral Feedback.** Each session will entail HIV prevention education (i.e., risk behaviors and prevention strategies) and behavioral goal setting to align the participant's goals with their current behaviors to evoke personal motivation to adopt and maintain HIV prevention strategies. Building on the goal setting of NCM using MI strategies, intervention youth will complete very brief daily diaries on their study-issued phone that populates an interface that provides visual feedback about how one's current behaviors align with their health goals. These daily diaries take less than 5 minutes to complete each day. The nurse then can use this visual to facilitate discussion about the barriers and facilitators that impeded or enhanced one's ability to actualize the uptake and adherence to HIV prevention strategies. The nurses will make monthly booster calls to intervention participants on the study issued phone in months 1-3 following the end of the face-to-face sessions. During this call, the nurse will inquire about the uptake and adherence to the HIV prevention strategies outlined during the NCM sessions, any other needs that they can address for the participant at that time, and will help the participant navigate services as needed.

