[name] will have primary responsibility for monitoring study research staff, who will receive training on the study design, recruitment, and protocol prior to study initiation. Research staff will receive formal training on the study protocol by Drs. [name], [name], [name], and [name], which will entail 2 weeks of intensive training session followed by additional training sessions as needed. The team will attend bi-weekly team meetings during data collection with the principal and co-investigators to discuss any study issues regarding recruitment and follow-up data collection and weekly meetings with [name]. These meetings will be used to discuss experiences with the intervention participants, provide consultation, ascertain whether the research staff are following study protocols, evaluate and reinforce cultural competence, and identify any potential adverse reactions. [name], study statistician, will coordinate data management and analysis. He will oversee development of data entry screens and the database development, supervise data entry verification, and work with the investigators in conducting all data analyses.

Follow-up face-to-face visits at 3, 6, 9, and 12-months will include a query of participants on whether they had “any serious health events that caused them to seek medical attention within the past 3 months” and if any of these resulted in “hospitalizations overnight.” Details of these events will be recorded.

Data Management. The research coordinator will monitor study data for completeness and accuracy weekly. Ongoing training and weekly quality assurance checks will be performed to ensure adherence to all study protocols including confidentiality. Survey data will be stored on hard drives of encrypted tablets and then uploaded to a desktop microcomputer master file daily. Individual data files are automatically merged with the master data set via REDCap. Weekly backups of these survey data set will be stored as an encrypted file and in a secure area physically remote from the data management area. All study related paper forms, surveys, and data will be destroyed by shredding after seven years. All necessary firewall and password protections will be implemented to restrict access and ensure data confidentiality.

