Adverse Event Reporting. Study participants will be encouraged to immediately report any "emergencies or events" by calling the study contact number. These instructions will be included on all instructions that are sent to participants, programmed into the study issued cell phones, and on the consent forms. The study team will record all reported events in the adverse events and unanticipated problems log (including the subject's name, date, and event description). All members of the study team will inform the principal investigator, [name] [name] immediately, of any adverse events and unanticipated problems who will consult with co-investigators and the safety monitoring committee members on the action. The PI will report the incident to the UTHealth IRB within one week. The action and date of implementation will also be recorded in the adverse event unanticipated problems log. The entire investigative team and monitoring committee will participate in classifying events as "serious" or "non-serious" (see list below), as well as "non-attributable," "possibly attributable" or "attributable" to the intervention (unlike a pharmaceutical trial where known side effects exist, the classification of "expected" vs. "unexpected" is inappropriate for this behavioral intervention). The SMC will advise the PI and the study team on actions to be taken to minimize further adverse events and unanticipated problems within 2 weeks of reviewing the reports.

1. Serious events include any event or condition that is life threatening, results in a hospitalization, cancer or a physical or cardiac event serious enough to require medical attention. These events may be:
 - a. Fatal
 - b. Life threatening

- c. Permanently disabling
- d. Required or prolonged hospitalization (Admission—not ER visit)
- e. Overdose
- f. Significant hazard to patient

2. Non-Serious events includes all other events.

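### The only active serious-event question looks back a fixed 3 months at visits 3 months apart, so missed or late visits leave periods unasked, and its use in remote follow-up is not stated.

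*Combined protocol and SAP*

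**What the plan says.** Under DSM Procedures, the plan states: "Follow-up face-to-face visits at 3, 6, 9, and 12-months will include a query of participants". The query concerns "any serious health events that caused them to seek medical attention within the past 3 months" and whether any of these led to an overnight hospital stay. The section Human Subjects Involvement, Characteristics, and Design gives the length of follow-up: "We will follow participants for 9 months after the intervention for a total study period of 12 months". The four visits are therefore the immediate post-intervention assessment and the 3-, 6- and 9-month follow-ups.

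The section Baseline and Follow-up Survey Data does not require those follow-ups to be in person. Surveys are "REDCap online surveys delivered on iPads or accessed remotely by participant smartphone or computer", and it adds: "For youth who leave the area during the data collection period, we will create an individualized survey link generated from REDCap". The section HIV/STI Test Specimens likewise allows, during COVID-19, an "At-home test to take under supervision of a study staff via video call".

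The other event route described for both arms is self-report. Adverse Event Reporting says: "Study participants will be encouraged to immediately report any" emergencies or events by calling the study number. In the intervention arm, the Intervention Description adds six nurse sessions and three monthly booster calls, and says that "at each session, the nurse will assess mental health, substance use, and housing needs".

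The answers matter to monitoring. The investigators' meetings every other week are to review the serious health events that participants report, and the Safety Monitoring Committee reviews adverse events quarterly.

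**The concern.** A look-back equal to the visit spacing covers the year only if every visit takes place on schedule. The plan does not expect that. It calls the population transient, assumes 30% attrition at 9 months and provides for youth who leave the area. No section lengthens the window after a missed or late visit, and none says that the question is asked when follow-up is remote.

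The youth most likely to miss visits or move away are thus the least completely asked. The plan counts hospital admission and overdose as serious, and its background section names overdose and suicide as leading causes of death in this population. Events in the unasked periods may not reach the team or the committee. Intervention youth also have extra nurse contacts in which an event may surface, while wait-list youth have none during follow-up, so the chance of learning about an event may differ by arm.

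**Working it through.** **Inputs.** Window: 3 months, fixed (DSM Procedures). Visits: months 3, 6, 9 and 12 (same section). Follow-up: 12 months. Attrition: 30% at 9 months (Sample Size and Power Calculations). No rate of intermittent missed visits is given anywhere.

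**The plan's own figure.** 450 × 0.70 = 315, with 300 × 0.70 = 210 and 150 × 0.70 = 105. This reproduces. It describes loss by the end of the study, not visits missed and followed by a return.

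**Coverage by attendance pattern.** Under the present wording, each attended visit covers the 3 months before it. Under a window back to the last completed survey, coverage runs from enrolment to the last attended visit.

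| Visits attended | Months asked about, present wording | Months asked about, since last completed survey |
|---|---|---|
| 3, 6, 9, 12 | 12 | 12 |
| 3, 9, 12 | 9 | 12 |
| 3, 12 | 6 | 12 |
| 12 only | 3 | 12 |
| 3, 6, 9 (then lost) | 9 | 9 |
| 3 only (then lost) | 3 | 3 |

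Even with all four visits attended there is no slack. A visit w weeks late, after a punctual one, leaves w weeks unasked.

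**Scenario A: intermittent misses (assumption).** Each of the four visits is missed independently with probability m.

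- Present wording: an interval is unasked when the visit that ends it is missed, so the unasked share is m.
- Since last completed survey: an interval is unasked only when the visit that ends it and all later visits are missed. For the last interval back to the first, the probabilities are m, m², m³ and m⁴. The unasked share is (m + m² + m³ + m⁴)/4.

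| m | Present wording | Since last completed survey |
|---|---|---|
| 0.1 | 10% | 0.1111/4 = 2.8% |
| 0.2 | 20% | 0.2496/4 = 6.2% |
| 0.3 | 30% | 0.4251/4 = 10.6% |

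**Scenario B: youth who do complete month 12 (assumption).** Each of the first three visits is missed independently with probability p. The share of completers with at least one 3-month gap is 1 − (1 − p)³, and the unasked time is 315 × 9 × p person-months.

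- p = 0.05: 14%, about 45 of 315 youth, 142 person-months.
- p = 0.1: 27%, about 85 youth, 284 person-months.
- p = 0.2: 49%, about 154 youth, 567 person-months.
- p = 0.3: 66%, about 207 youth, 851 person-months.

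The reworded question would recover all of this time.

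**Scenario C: dropout without return (assumption).** Let cumulative loss at the four visits be 7.5%, 15%, 22.5% and 30%. The unasked share is (7.5 + 15 + 22.5 + 30)/4 = 18.75% under either wording. The rewording gains nothing here.

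**Remote follow-up.** No rate applies, so the sections are set side by side. DSM Procedures ties the question to face-to-face visits. Baseline and Follow-up Survey Data allows the same follow-ups by remote access or link. The Measures section lists follow-up survey content and names no serious-event item. If the question were not carried into remote surveys, a youth followed only remotely would have 12 of 12 months unasked. The text leaves this open.

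**The case against.** A reader might infer four stronger conclusions, which the documents do not support.

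First, that 30% of follow-up goes unasked because the plan assumes 30% attrition. That figure is loss by 9 months, which the plan itself calls very conservative beside 88–89% retention in other studies. It is not a per-visit miss rate, and under pure dropout the rewording recovers nothing.

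Second, that remote participants are not asked at all. DSM Procedures says that face-to-face visits include the query; it does not say that only they do. The list in Measures is not exhaustive, since process items are added to a survey elsewhere, and an RA contacts link users to see the survey completed. The defect is silence, not a stated exclusion.

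Third, that events in the gaps would be missed. Reporting instructions appear on consent forms and on all instructions sent to participants as well as on phones, participants may use their own phones, RAs are on site weekly, and testing is offered to both arms at each time point. None of these contacts carries a stated serious-event question, and study phones are not replaced when lost (12% lost or damaged in an earlier study). What can be said is that events may be missed.

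Fourth, that by-arm safety counts will be biased. The items listed for the committee include a demographic comparison of arms but no by-arm event counts, and unequal nurse contact is inherent in a wait-list design. Unequal detection is a reasonable inference, not a flaw in a planned analysis.

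A short fixed recall period can also be defended as limiting recall error in a trial classed as minimal risk. That is a real trade-off, but it does not explain leaving the time before a missed visit unasked. The arithmetic of the missed and late visits stands.

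**Conclusion.** The gap is real and follows from the wording: 3 months unasked for each visit missed before a return, w weeks for a visit w weeks late, and 6 of 12 months for a youth seen only at months 3 and 12. Whether remote follow-up carries the question is unstated and needs to be settled in the text.

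How much this matters in total depends on an intermittent-miss rate that the documents do not give. With independent misses at 0.1, 0.2 or 0.3 per visit, the change would cut the unasked share from 10%, 20% or 30% to about 3%, 6% or 11%; with permanent dropout there is no gain. The point concerns the completeness of safety ascertainment. It changes no sample size, power or alpha. The correction should be made because it is specific and cheap.

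**What to change.** In DSM Procedures, change the look-back to *since your last completed study survey (or since enrolment)* and record the date of each event. Put both items, the serious-event question and the overnight-hospitalisation question, in the REDCap follow-up survey, so that they are asked in every mode of contact and in both arms. State there that remote and link-based follow-ups include them.

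If events are tabulated by arm, base the comparison on this common query and list separately the events first learned at nurse sessions or booster calls. That table is optional, since the plan does not now promise one.

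The cost is two reworded survey items, a date field and, if by-arm tables are made, one extra row. The downside is slightly longer recall for youth who missed visits. The change does not reach youth who never return.

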While participants will be assured that their participation will not affect health and social services being provided at any location, some participants may feel concerned about or pressured to be part of the study. We will verbally assure participants at the beginning of each NCM session and at each follow-up that their participation is voluntary and that they can participate in all, part of, or none of the session and can withdraw from the study at any time for any reason without penalty.

Adverse Event Identification. Survey questions and nurse case management sessions might create awkwardness or discomfort due to the potential for disclosing or discussing risk behaviors. A potential risk in participating in the proposed research is becoming more aware of and/or reporting past events, current circumstances, thoughts and feelings, and risk behaviors that may make participants feel uneasy. The research staff will receive 4 weeks of training prior to initiating recruitment procedures for this study to assure that all protocols and procedures are followed. Research staff will have ongoing supervision in how to handle awkwardness, embarrassment, or discomfort. Participants can choose whether to be in the study or not. They may withdraw at any time without consequences of any kind. They may also refuse to answer any questions they do not wish to answer and still remain in the study. It is possible that there may be occasions when study participants exhibit stronger and more serious signs of emotional distress; we may encounter individuals who express suicide intent, have psychiatric emergencies, or exhibit other indicators of acute distress. Research staff will be trained to identify signs of acute distress or suicidal ideation and trained how to respond if they occur. We will emphasize to research staff at all study team meetings that if a participant becomes upset, they should be offered the option of discontinuing participation in the study without penalty (i.e., still receiving payment) or continuing at a later time after a break. Further, the computer assisted survey administration limits participant exposure to potentially sensitive items. For example, participants who have not engaged in a certain risk behavior, such as substance use, are not exposed to more detailed questions about use. Participants will also be informed that they may skip any item that makes them feel uncomfortable. In the event of any acute emotional distress, research staff will remain with the participant until s/he is no longer distressed.

The Covenant House Texas (CHT) shelter, where some of the NCM intervention sessions may be conducted when preferred by the participant, has 24-hour staff trained in managing acute episodes of distress and psychosis. CHT shelter has a clinic staff by Baylor College of Medicine Pediatric Resident in their Adolescent Fellowship on the premises with a clinical psychologist and a psychiatrist on staff. The Salvation Army (SA) drop-in center has social work staff available during business hours who are trained in managing acute episodes of distress and psychosis. SA has a Healthcare for the Homeless Program clinic that operates 1-2 days a week. We will follow the mental health safety protocols of the shelter and drop-in center to manage any participant needs including acute mental health needs that may arise during the study. Individuals who wish to pursue follow-up care will also be given a referral list specifically tailored

to the individual's request. We will have prepared referral lists for perpetrators and victims of abuse as well as for common psychological issues. At the end of each assessment, all participants will be offered a list of relevant, local referrals. We will not be asking about suicidal ideation during the study, so it is unlikely that we will encounter acute suicidal ideation. However, given the risk of suicide and mental health issues within the population, we have strict protocols in place for handling mental health concerns that arise among subjects during the study. As well, anyone having direct involvement with the participants will be fully trained by the PI and the partnering recruitment agencies in procedures for assessment and intervention in cases where suicidal ideation is expressed. The nurse interventionists have additional institutional policies and procedures in place they will follow to assure swift and safe response to an acute mental health crisis. This may include both in-patient and out-patient follow-up mental healthcare. In case of an adverse mental health event, regardless of whether it is related to the study, research staff will be instructed to immediately contact the shelter or drop-in center staff to implement already in place protocols for managing youth expressing suicidal ideation and to contact the PI and take appropriate clinical action in these circumstances to assure participant and staff safety including referral to another level of clinical care. All study staff will be trained to immediately notify recruitment site staff and facilitate implementation of protocols for care in cases of acute mental distress. Our experienced MD supervisors (Drs. [name] and [name]) and [name] will be available for immediate consultation in the event of encountering an unexpected acute psychological issue; and as part of their training, research staff will be made familiar with referral resources and procedures for local psychological, social service, and other emergency care needs.

Adverse Event Reviewing. Adverse events will be reviewed at each study team meeting to assure all participant safety and reporting protocols were followed. Reports of all Adverse Events and unanticipated problems will be The SMC will meet prior to participant enrollment and then meet quarterly to review reports on adverse events and unanticipated problems, discuss participant safety concerns, and review general study progress.

Adverse Event Reporting. Study participants will be encouraged to immediately report any "emergencies or events" by calling the study contact number. These instructions will be included on all instructions that are sent to participants, programmed into the study issued cell phones, and on the consent forms. The study team will record all reported events in the adverse events and unanticipated problems log (including the subject's name, date, and event description). All members of the study team will inform the principal investigator, [name] [name] immediately, of any adverse events and unanticipated problems who will consult with co-investigators and the safety monitoring committee members on the action. The PI will report the incident to the UTHealth IRB within one week. The action and date of implementation will also be recorded in the adverse event unanticipated problems log. The entire investigative team and monitoring committee will participate in classifying events as "serious" or "non-serious" (see list below), as well as "non-attributable," "possibly attributable" or "attributable" to the intervention (unlike a pharmaceutical trial where known side effects exist, the classification of "expected" vs. "unexpected" is inappropriate for this behavioral intervention). The SMC will advise the PI and the study team on actions to be taken to minimize further adverse events and unanticipated problems within 2 weeks of reviewing the reports.

1. Serious events include any event or condition that is life threatening, results in a hospitalization, cancer or a physical or cardiac event serious enough to require medical attention. These events may be:
 - a. Fatal
 - b. Life threatening

- c. Permanently disabling
- d. Required or prolonged hospitalization (Admission—not ER visit)
- e. Overdose
- f. Significant hazard to patient

2. Non-Serious events includes all other events.

A few potential minimal risks to subjects exist such as breach of confidentiality or normal risks associated with having a phone. Breach of confidentiality is not believed to present any significant risk given the data protections described above. However, to mitigate this risk we have outlined steps we will take to protect confidentiality in the Human Subjects sections, **Safeguarding Confidentiality and Certificate of Confidentiality**. Before data collection is initiated, researchers will obtain a Certificate of Confidentiality from NIH to protect participants from the requested release of study data. All participants will be informed that this certificate has been obtained, and what protections it affords them during the informed consent process. Participant data will not be released to any party outside the research team.

Potential Risks.

There are no physical risks associated with participation. The risk of psychological distress is related to the potential of receiving a positive HIV or STI test result. The types of study questions concerning past events, current circumstances, thoughts and feelings, sexual behaviors, substance use, and sexually transmitted infections may cause distress. Participants may find thinking about and answering questions about these issues upsetting; these questions will be asked in as sensitive a manner as possible. While participants will be assured that their participation will not affect health and social services being provided at any location, some participants may feel concerned about or pressured to be part of the study. Another potential risk is the loss of confidentiality or disclosure of information or data about the participant. While there were no reported adverse reactions to Nurse Case Management in our previous studies, there is the potential of stress and negative reactions from the self-reflection during the sessions.

For data collection, participants may find thinking about thoughts and feelings that arise or answering questions about these issues upsetting; these questions will be asked in as sensitive a manner as possible. As well, if a participant answers no to a sexual activity question, they would not receive additional, more details questions about sex. By tailoring the questions, we minimize the exposure to sensitive questions and reduce the burden and fatigue that may arise from taking a survey. We use ACASI computer-based surveys to allow participants to read and answer the questions privately and not have to hear them aloud or tell another person, which may reduce any possible distress associated with answering the questions. While participants will be assured that their participation will not affect health and social services being provided at any location, some participants may feel concerned about or pressured to be part of the study. We will verbally assure participants at the beginning of each NCM session and at each follow-up that their participation is voluntary and that they can participate in all, part of, or none of the session and can withdraw from the study at any time for any reason without penalty. Another potential risk is the loss of confidentiality or disclosure of information or data about the participant. We have detailed below extensive measures to ensure confidentiality and decrease the risk for disclosure of private information.

During data collection, participants may refuse to answer any questions that make them feel uncomfortable. Participants may discontinue participation in the study at any time. We anticipate that the types of adverse experiences that may occur, if any, may be associated with issues

arising during data collection. None of these risks are considered significant. Having a study phone poses no more risk than having a personal phone.

This is a single site study.

Ongoing assessments that may impact safety or ethics of the study

The research team is active in HIV prevention research and will continue to monitor the literature, attend national and international conferences, and consult with colleagues to assure that we are aware of any emerging data that may impact safety or the ethics of the study.

Advanced plans for interim/futility analysis

One focus of the investigator meetings will be to continuously monitor and develop strategies to prevent adverse reactions, monitor the research staff, and protect data integrity. Accrual data will be reviewed by the team and the UTHealth IRB. The study team will make amendments to the protocol should accrual fall below 15% of the target, or should drop-outs exceed projections by 15%. This will include the addition of recruitment sites.

Statistics

Randomization. Participants will be randomly assigned to the intervention or wait list control arm using a computer-generated blocked 2:1 allocation; 300 participants will be in the intervention arm and 150 will be in the wait list control arm (see Figure 3). Participants will be told which group they are in after completing the baseline survey and will receive a study-issued phone with programmed YEH resources unless they prefer to use their own phone. In this case, the behavioral feedback app will be loaded onto their personal phone for those in the intervention arm, and these youth will be provided with a list of YEH services.

Study Design.

| | Baseline | Intervention | 3 Mon. | 6 Mon. | 9 Mon. | Intervention |
|-------------------|----------------|------------------|----------------|----------------|----------------|--------------|
| Treatment arm | O ₁ | X O ₂ | O ₃ | O ₄ | O ₅ | |
| Wait list control | O ₁ | O ₂ | O ₃ | O ₄ | O ₅ | X |

Sample Size and Power Calculations. The primary endpoint is the efficacy of NCM to increase PrEP and nPEP uptake, HIV testing, STI screening, and condom use. Conservatively assuming an attrition rate of 30% at 9 months, the final sample size will be 315, with the 2:1 randomization allocation providing for 210 participants in the intervention arm and 105 in the control arm. We estimate a retention rate of 70% based on study resources, community partnerships and support, the use of study-issued phones, the use of increasing follow-up incentives. This retention rate is substantially lower than the rate reported for other longitudinal YEH studies that have retained 88-89% ^{13,14} of youth to be very conservative in our retention estimation.

Table1. Outcome Measures by Study Aim

| Construct | Scale/Measure | Alpha |
|-----------------------|---|-------|
| Aim 1 Outcomes | | |
| PrEP/nPEP Uptake | PrEP uptake; nPEP uptake (NCM report, chart review) | NA |
| Condom Use | Youth Risk Behavior Survey; ¹ (condom use at last sex) | NA |
| HIV/STI Test Uptake | Rapid HIV test; Gonorrhea, Chlamydia, Syphilis test | NA |
| Aim 2 Outcomes | | |
| Mental Health | Brief Symptom Index-18 ^{2,3} | 0.80 |
| Housing Status | In a shelter, apt/house, with someone, outside, in a car...? | NA |
| Substance Use | TCU Drug Screen II ^{4,5} | 0.89 |

| Exploratory Outcomes (possible mediators based on CHSCF; see Figure 1) | | |
|--|---|------|
| Healthcare Engagement | Healthcare clinic visit adherence ⁶ | NA |
| Condom Use Self-Efficacy | Condom Use Self-Efficacy Scale ⁷ | 0.91 |
| HIV Risk Perception | Perceived Risk of HIV scale ⁸ | 0.88 |
| PrEP Facilitators & Barriers | Facilitators and Barriers to PrEP Use ⁹ | NA |
| Health Seeking | General Help Seeking Questionnaire ¹⁰ | 0.83 |
| Coping | Coping Inventory for Stressful Situations-Adolescent ^{11,12} | 0.92 |

For Aim 1, we anticipate having 87% power (95% CI: 84.8, 89.0) to detect the intervention effect on the reduction of condomless sex. Alpha was set at .05 and the power calculation was conducted using the SIMR package¹⁵ by 1000 Monte Carlo simulations with a generalized linear mixed model design that included a random intercept per participant. Data for the simulation were generated with compound symmetric covariance structure in the SIMSTUDY package by assuming that 79% of participants are sexually active and the probability of condomless sex will reduce modestly from 0.7 to 0.4 in the intervention group. The probability was conservatively assumed to decrease to 0.55 in the control group due to the potential for a placebo and/or contamination effect. The effect sizes and powers for HIV testing and STI screening and treatment outcomes are anticipated to be of similar magnitude to the condomless sex outcome. For the PrEP uptake outcome, it was assumed that rates would change from 2% to 4% in the control group and to 24% in the intervention group, for which the simulation resulted in 99% power (95% CI: 94.6, 99.9). Power analysis for the continuous instrument scores of Aim 2 indicates that a sample size of n = 315 will provide 80% power for the interaction of time and arm in a repeated measures model when the effect size is f= .11, a small effect size. This calculation assumes a correlation between repeated measures of r = .50.

